3.2.5.4.3. RADIOGRAPHIC ASSESSMENTS

For the purposes of data capture, the following radiographic assessments will be made by two independent musculoskeletal radiologists at the core lab. A third independent radiographic reviewer will adjudicate in instances of disagreement. The radiographic assessments will include:

- Intervertebral Angle;
- Change in Intervertebral Angle;
- Horizontal Translational;
- Change in Horizontal Translational;
- Global Range of Motion;
- Change in Global Range of Motion;
- Disc Height (assessed by determining Functional Spinal Unit [FSU] height and by directly measuring height of disc space)
- Change in Disc Height;
- Disc Angle;
- Change in Disc Angle;
- Spondylolisthesis;
- Change in Spondylolisthesis;
- Device Condition;
- Device Bending;
- Device Breaking;
- Device Fracture;

- Device Subsidence (can also be derived with FSU Height);
- Device Migration;
- Device Protrusion;
- Radiolucency;
- Heterotopic Ossification;
- Bridging Bone;
- Maintenance of PreOp Motion;
- Osteophyte Formation;
- Endplate Sclerosis;
- Kellgren-Lawrence Adjacent Level Disc Degeneration;
- Facet Degeneration;
- Stenosis;
- Modic Changes;
- Cysts and
- Additional Observations.

This in vivo endplate thickness analysis will analyze a consecutive series of the first 25 subjects who complete the 24 month visit and any subject with an explant and/or SAE/severe AE that is judged to be implant-associated or implant/surgical procedure-associated. The analysis will be performed using available x-rays from the discharge, 12 Month, 24 Month visits and annually thereafter as set forth in the core lab protocol.

3.2.5.4.4. [REDACTED]

[REDACTED]

[REDACTED]

[REDACTED]

[REDACTED]

- [REDACTED]
- [REDACTED]
- [REDACTED]
- [REDACTED]
- [REDACTED]

3.2.5.4.5. STUDY COMPLETION, TERMINATION OR LOSS TO FOLLOW-UP

Subjects are expected to remain in the study for at least 24 months following treatment.

Subjects who complete their 24 month visit prior to the last study subject's completion of the 24 month visit will continue to be followed annually until the last subject enrolled has completed the 24 month evaluation. Subjects will continue to be followed thereafter until follow-up is no longer required by FDA. However, for the purpose of primary safety and efficacy evaluations, the study completion/ termination assessment will be made at 24 months postoperatively, or at earlier time point if the subject withdraws or is withdrawn from the study. Missed patient evaluations after the point of withdrawal will not be considered protocol deviations.

Subjects may be withdrawn from a clinical study early due to withdrawal of Informed Consent, death, lost to follow-up, or Investigator medical decision. Each premature termination from the study must have the reason for their withdrawal from the study documented in both the source documents and on the applicable case report form.

In the event of a secondary index surgery requiring removal of a spinal system, every effort will be made to retrieve the explanted device for analysis. The instructions for the surgical technique for device removal of the Simplify Disc are included in the Investigator and Study Manuals. Any subjects with either or both of the Simplify Discs removed will be followed, but follow-up subsequent to these events will be summarized separately, if the subject has not withdrawn consent.

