Subjects who complete their 24 month visit prior to the last study subject's completion of the 24 month visit will continue to be followed annually until the last subject enrolled has completed the 24 month evaluation. However, for the purpose of primary safety and efficacy evaluations, the study completion/ termination assessment will be made at 24 months postoperatively, or at an earlier time point if the subject withdraws or is withdrawn from the study.

Follow-up evaluations annually after 24 months will include:

- AP and lateral X-rays (plain films);
- Flexion-extension X-rays (used to determine range of motion);
- Lateral bending films;
- Radiographic core lab evaluations;
- Postoperative subject survey (medication and satisfaction)
- Dysphagia Handicap Index;
- NDI assessment;
- SF-36 Health Survey;
- Neck and arm pain questionnaires (neck, arm, left arm and right arm);
- Foraminal compression test;
- Physician perception of results;

- Neurologic evaluation;
- Gait assessment;
- Study related medications;
- Work status;
- Adverse events as defined by Section 3.2.6.1 and Section 3.2.7 of this protocol and.
- [REDACTED]

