missing at random (MAR)³⁰ which is a much weaker assumption than missing completely at random (MCAR) which requires unconditional independence. Although MAR is likely to hold in many more situations than MCAR, in any given situation there is no way to confirm whether the assumption of MAR is tenable and consequently, whether or not the MI analysis produces valid inference. For this reason, a complete case analysis followed by a tipping point sensitivity analysis will be conducted in sensitivity analyses (see below). MI will be used to impute missing final NDI in patients otherwise evaluable for primary CCS. For each imputation, the composite endpoints would be constructed from the imputed NDI values and within randomly completed data sets, the device group difference and standard error is determined. For these imputations, the status of the other CCS components will be based on available data up to the point of loss-to-follow-up which is essentially a last-observation-carried forward approach. In this case, the patient's Month 24 secondary surgical intervention status, major device-related complication status, and neurological success status will be inferred from their Month 12 status. Imputations for NDI will be repeated 20 times to produce 20 randomly completed data sets. The final device group difference will be the average of the multiple imputed datasets and its standard error will account for both within (usual) and between imputation error as described in Rubin and Schenker 1991. The MI standard error will be used in the derivation of the p-value to test the non-inferiority hypothesis. MI analyses will be performed using SAS³¹ Proc MI and MIANALYZE or their equivalent.

A complete case analysis followed by a tipping point analysis will be conducted to complement the primary MI approach in order to evaluate the robustness of statistical conclusions to the assumptions inherent in MI analyses. This includes the untestable assumption; namely, that the probability that a value is missing is independent from the value itself conditional on baseline values and clinical status up to the point. In a tipping point analysis, missing values in each group are separately assumed to be either successes or

³⁰ Rubin DB Inference and missing data. Biometrika 1976, 63:581-592.

³¹ SAS Institute, Cary NC.

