3.6.3. DATA COLLECTION

Data will be compiled using an Electronic Data Capture system operated by the Independent Monitoring Organization. The Clinical Monitor will verify that appropriate data is recorded for all study subjects for whom Informed Consent is obtained; and that no study treatments are administered without Informed Consent. Documentation will be provided for study subjects who choose to terminate study participation and for subjects terminated by their physicians. A full explanation of the reasons for non-participation will be provided.

All CRF information should be traceable to source documents. Surveys completed by the patient will be considered source documents. Other records that will be considered source documents are hospital records, clinic charts, x-rays, CTs, MRIs and DEXA scans. Copies of source documents that may be collected by NuVasive include, but are not limited to: signed and dated patient informed consent documents (redacted); operative summaries; hospital discharge summaries/orders; any relevant progress notes pertaining to AEs, reoperations, or deaths; and autopsy reports. In cases where assessments (e.g., foraminal compression test, neurological examination) are not dictated in the patient's clinical charts or documented on source worksheets, these CRFs will also be considered source documents. Surveys collected by tablet (if used) do not require source documents.

Data will be reviewed to identify inconsistent or missing data, Serious Adverse Events, and Unanticipated Adverse Device Effects. Data problems will be addressed in calls to the investigational sites and during site visits. Electronic Case Report Forms and data files will be secured to ensure confidentiality. Quality assurance procedures are designed to ensure that complete, accurate and timely data are submitted, that protocol requirements are followed, and that complications and adverse events are reported as required under Section 3.2.6.1 and Section 3.2.7 of this protocol.

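### An investigator may withdraw a consenting implant patient by medical decision, with no criteria and no provision to keep collecting outcomes to Month 24

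*Combined protocol and SAP*

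**What the plan says.** Section 3.2.5.4.5 (Study Completion, Termination or Loss to Follow-Up) lists four routes out of the study: "Subjects may be withdrawn from a clinical study early due to withdrawal of Informed Consent, death, lost to follow-up, or Investigator medical decision". The fourth has no criteria. For the primary evaluations, the completion or termination assessment is made at 24 months "or at earlier time point if the subject withdraws or is withdrawn from the study"; section 3.2.5.4.2 says the same. The section adds: "Missed patient evaluations after the point of withdrawal will not be considered protocol deviations". Section 3.6.3 (Data Collection) confirms that the route is expected to be used, since it calls for documentation "for subjects terminated by their physicians".

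One group is explicitly kept under observation: "Any subjects with either or both of the Simplify Discs removed will be followed, but follow-up subsequent to these events will be summarized separately", provided consent has not been withdrawn. Nothing similar is stated for a consenting patient whom the investigator withdraws.

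Section 3.2.6.8 makes multiple imputation the primary method. It imputes final NDI only, in patients who are otherwise evaluable. The other three components of composite clinical success use data up to the point of loss, with Month 24 status inferred from Month 12; the plan itself likens this to last observation carried forward. A complete-case analysis with a tipping-point analysis is the sensitivity analysis.

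**The concern.** In a drug trial, a medical decision to withdraw may stop an ongoing treatment. Here the discs are already implanted, and withdrawing the patient from the study leaves them in place. What stops is mainly the collection of data. The protocol already accepts that a failed device is no reason to stop following a patient, because explanted patients are followed, but it does not extend that to patients withdrawn by the investigator.

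Three things are at stake.

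- **Late events.** A patient withdrawn at Month 13 and reoperated at Month 18 would enter the primary test as free of secondary surgery, with no imputation uncertainty on that component. The same holds for an implant-associated SAE after withdrawal.
- **Informative missingness.** The reason for withdrawal is medical, so it may be related to outcome. Every prospective patient receives the device, so the person deciding always knows the treatment. The control data come from a completed trial, so this rule can add missing data only to the device arm.
- **Avoidable loss.** Section 3.2.6.8 names prevention through study conduct as the first approach to missing data. This rule works against that.

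**Working it through.** **1. The plan's own figure.** Inputs from section 3.2.6.4: control rate 0.700, expected difference 0.035 (device 0.735), margin -0.10, one-sided alpha 0.05, 128 controls and 154 device patients evaluable. (The text also gives a device rate of 75.0%, but the software statement rests on 0.735, which is used here.)

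SE = sqrt(0.70 × 0.30/128 + 0.735 × 0.265/154) = 0.0539

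Power = Φ((0.10 + 0.035)/0.0539 − 1.645) = Φ(0.86) = 80.5%. The plan states 80%.

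154/0.85 = 181.2, rounded up to 182. This matches the plan and leaves 182 − 154 = 28 device patients allowed to be without an endpoint.

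**2. Assumptions the documents do not supply.** Let k of the 182 device patients be withdrawn by medical decision, with true Month 24 success q between 0 and 0.5. Suppose they are in effect imputed at the rate of the remaining device patients. Controls are unaffected; 154 and 128 patients are evaluable.

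**3. Overstatement of the device rate at the design rate.** Bias = (k/182) × (0.735 − q).

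For k = 5: (5/182) × 0.735 = 2.0 points at q = 0, and (5/182) × 0.235 = 0.65 points at q = 0.5.

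**4. One-sided error at the margin** (true device 0.60, control 0.70). With f = k/182, the remaining patients' rate is r = (0.60 − f·q)/(1 − f), and

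error = Φ((0.10 + r − 0.70)/SE − 1.645), with SE = sqrt(0.70 × 0.30/128 + r(1 − r)/154).

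For k = 5, q = 0: r = 0.60/0.9725 = 0.6169, SE = 0.0563, error = Φ(0.30 − 1.645) = 9.0%.

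For k = 5, q = 0.5: r = (0.60 − 0.0137)/0.9725 = 0.6028, SE = 0.0565, error = Φ(0.05 − 1.645) = 5.5%.

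| k | Error, q = 0.5 | Error, q = 0.25 | Error, q = 0 |
|---|---|---|---|
| 2 | 5.2% | 5.8% | 6.3% |
| 5 | 5.5% | 7.1% | 9.0% |
| 9 | 6.0% | 9.3% | 13.8% |

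**5. How to read these.** For a given k and q they are upper bounds. The calculation lets nothing observed before withdrawal lower the imputed success, and it ignores failures already recorded. If withdrawn patients do as well as the rest, the effect is nil.

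**The case against.** A reader might infer that such withdrawals break the missing-at-random assumption. The documents do not support that. Section 3.2.6.8 defines the assumption as requiring that "the probability that a value is missing is independent from the value itself conditional on baseline values and clinical status up to the point". Withdrawal prompted by a poor course that is already in the data is compatible with it; the assumption fails only if the decision rests on information outside the data. NDI and neurological status are collected at 6 weeks and at 3, 6 and 12 months, and an assessment is foreseen at withdrawal. This part of the objection stands.

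It also stands that the whole outcome is not imputed. Only final NDI is. An index-level surgery or implant-associated SAE seen before withdrawal remains a failure whatever NDI is drawn.

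The no-deviation sentence might be read as an order to stop collecting data. It is deviation accounting for every kind of withdrawal and neither requires nor forbids collection. The gap is that nothing else in the section asks for it.

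The tipping-point analysis runs through all assignments, including every missing device patient as a failure and every missing control as a success. Section 3.2.6.15 adds a listing of adverse events in patients who discontinued early and a discussion of possible drop-out bias, and each withdrawal reason must be documented. These are real safeguards but partial ones. The tipping-point analysis does not drive the primary conclusion, treats all missing patients alike, and sets no number for how small the fraction of changed conclusions must be. Neither it nor the listing can recover an event nobody recorded.

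Finally, the explant comparison does not bear on the primary result, since secondary index surgeries are already failures. It shows only that continued follow-up is considered feasible.

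**Conclusion.** The gap is real and worth closing; it is an avoidable weakness in conduct, not a flaw that invalidates the primary analysis. The plan does not separate investigator-decided withdrawal from withdrawal of consent, and makes no stated provision to obtain Month 24 outcomes after the former. Later failures and safety events in those patients can then be missed in the primary test and the safety record. The plan also names no substitute for Month 12 status when withdrawal comes before Month 12, beyond a general reference to available data.

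Size is uncertain. With 5 such patients and true success of 0 to 50%, error at the margin is about 5.5% to 9% as an upper bound, assuming controls are unaffected.

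A reader might go further and conclude that these patients are probably failing and that the bias favours the device. Neither is established. The documents give no frequency of, or reasons for, medical-decision withdrawals. The control trial's withdrawal rules are not shown, some controls are known to be unevaluable, and section 3.2.6.4 assumes only 85% of selected controls are complete. A similar rule there could partly offset the effect.

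**What to change.** In section 3.2.5.4.5:

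- Separate investigator-decided withdrawal from withdrawal of consent.
- State that, unless the patient withdraws consent, dies or is lost to follow-up, NDI, neurological status, secondary surgeries and SAEs continue to be collected to Month 24, remotely where possible.
- Limit the no-deviation sentence to the same three situations, and align the matching text in sections 3.2.5.4.2 and 3.6.3.

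This changes data collection only, not clinical care, and uses assessments already in the schedule. The cost is protocol wording and a few extra contacts for what should be a small number of patients.

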3.2.4. STUDY DESIGN

3.2.4.1. OVERALL STUDY DESIGN

Each site will be asked to target a minimum of 10 subjects depending on patient availability. Each US site will not be permitted to enroll more than 25 subjects (includes one training subject). The first procedure at each site will constitute a training set. Data from the training set will be summarized separately and not used in the primary comparison to control.

Investigators will use an anterior surgical approach. Surgeons will be trained on the technique, selection criteria, and protocol for the two-level Simplify Disc clinical study prior to their first implantation procedure.

Subjects will be considered enrolled in the study for the purposes of an intent-to-treat analysis, only after they have been treated as determined by the recording of time of incision.

Subjects excluded prior to treatment, due to withdrawal of consent, arising medical difficulties (e.g., heart attack), documentation of ineligibility by circumstances unforeseen at the time of Consent, etc. will be considered screening failures. Baseline data, including the reason for exclusion, will be collected for screening failures. However, baseline data for screen failures may not be complete, as the patient may be determined to be a screen failure early in the screening process. All patients enrolled in the study with a time of incision will be included in the "intent to treat" analysis set, regardless of failure to complete the required follow-up examinations.

All radiographic endpoints, including in vivo endplate thickness analysis, will be evaluated independently by one core laboratory. Range of Motion will be measured by this core lab using a protocol to determine this measurement incorporating validated techniques to ensure reproducibility.

Neurologic status will be evaluated by a qualified evaluator, who may be an MD, an RN or a PA.

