3.2.6. STATISTICAL CONSIDERATIONS

3.2.6.1. PRIMARY ENDPOINT

The study hypothesis is that in subjects with intractable radiculopathy (arm pain and/or a neurological deficit) with neck pain or myelopathy due to abnormalities localized to the levels of the two contiguous disc spaces at two contiguous levels from C3 to C7 that is unresponsive to conservative management, the Month 24 composite clinical success (CCS) rate of the two-level Simplify Disc will be no worse than conventional two-level ACDF when success is evaluated at Month 24.

Individual success for both the investigational and control groups is defined as:

- Neck Disability Index (NDI) score improvement of at least 15 points from pre-operative;
- Maintenance or improvement in neurological status^{15, 16};
- No serious adverse event classified as implant associated or implant/surgical procedure associated; and
- No additional surgical procedure classified as a “failure.”

Overall success will be determined based on data collected during the initial 24 months of follow-up. Each element of the neurological study exam will be evaluated for maintenance or improvement.

All secondary index surgeries will be classified as failures.

Per FDA Guidance for the Preparation of IDEs for Spinal Systems, the following definitions apply:*

15 Maintenance or improvement in neurological status will be based on motor, sensory, and myelopathic gait assessments.

16 Due to COVID-19, not all 24M visits (entire or portion) are able to occur in-person. If a 24M in-person visit does not occur, the 12M result will be carried forward to represent unavailable 24M results in the primary endpoint and subsequently adjudicated by the CEC.

- Reoperation - any surgical procedure at the index level(s) that *does not involve* modification, addition or removal of any components of the device and is not considered a removal, revision, or supplemental fixation.
- Revision – any procedure in the postoperative or follow-up period that adjusts or in any way modifies either one or both of the original implant configurations (e.g., adjusting the position of the original configuration, removal with replacement with same type of study implant).
- Removal – a procedure that removes one or more components of the original implant configuration without replacement with the same type of trial implant.
- Supplemental fixation – a procedure at the index level(s) in which additional spinal devices not approved as part of the protocol are placed.

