that takes place prior to seeing any outcome data (Rubin 2008)²⁵". At its conclusion, verification of balance between device groups within sub class will be done through easily interpretable graphical means.

Given the expected similarity of the populations from which the investigational and control groups will be obtained and the specificity of the clinical indication, it is expected that no more than 20% of the ACDF controls will require trimming. The sample size analysis described below accounts for up to 20% trimming of ACDF. It is assumed that no investigational device patients will be trimmed and so no adjustment for investigational device trimming is included in the sample size analysis. Should there be investigational device trimming, it is expected that the number of investigational device patients requiring trimming will be very small with no appreciable effect on statistical power.

We acknowledge that because the proposed propensity score design can only assess the comparability of the two groups after the prospective enrollment has been completed, there can be significant risk that in the end the data may not be comparable. The sample size determination accounts for up to 20% of the ACDF subjects to be trimmed in the iterative heuristic used to construct PS sub classes that meet Rubin's validity criteria. The risk of insufficient sample sizes due to more than 20% control group trimming can be mitigated by continuing enrollment into one the investigational device group should this be needed to obtain the required sample sizes for 80% power to reject the non-inferiority null hypothesis.

An evaluation of the variable collected in the [REDACTED] study indicate that all component variables necessary to formulate the relevant composite clinical endpoints will be available. Any differences in endpoint evaluation are due to the nature of the difference between artificial discs and fusion procedures. The components of the CCS will be evaluated in the same fashion for the ACDF control as they are to be evaluated for Simplify Disc enhancing comparability of results from the two studies. Although composite clinical success requires a threshold improvement in the Neck Disability Index (NDI), the "NDI is the oldest and most

25 Rubin D. For objective causal inference, design trumps analysis. The Annals of Applied Statistics 2008, 2:3:808-840.

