3.2.6.5. ANALYSIS SETS

The study contains two treatment arms with patients receiving either two-level Simplify Disc or two-level ACDF. The following subject groups or analysis sets will be used to complete the analysis of data.

- Intent-to-treat (ITT) analysis set: The ITT analysis set will include all enrolled patients in which treatment was attempted as defined by the recording of incision time and excluding training cases. Patients will be included according to their intended treatment device. Since the investigational and control treatments are to be performed at different institutions, it is not possible for subjects to receive the alternative treatment. Therefore, the ITT analysis set will be used in safety analyses.

- Primary Effectiveness (PE) analysis set: The PE analysis set includes all subjects in the ITT analysis set that are selected into a propensity score subclass. Primary effectiveness analyses will be conducted using the PE analysis set. Selection into a PS subclass is the observational study equivalent to being randomized. Intraoperative failures will be included in primary non-inferiority testing as composite clinical endpoint failures. Patients with no follow-up subsequent to surgery will be treated as having a missing primary composite clinical endpoint and will be handled according to the approaches outlined below.
- Per protocol (PP) analysis set: The PP analysis set will include patients in the PE analysis set that have no major protocol deviations including clinically significant deviations from inclusion or exclusion criteria. Secondary efficacy analyses will be performed using the PP analysis set.
- Training cases analysis set: Training case safety and effectiveness data will be summarized separately.
- Original Protocol (OP) analysis set: All patients enrolled in the original protocol prior to approval of the subject protocol with the [REDACTED] historical control will be analyzed separately to determine if they would meet the current patient enrollment criteria. OP safety and effectiveness will be summarized separately and compared to the ITT analysis set. Please note, due to the small sample size, these comparisons will lack statistical strength and will be provided for informational purposes only.

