3.2.6.13. SECONDARY EFFECTIVENESS ENDPOINTS

Secondary endpoints include:

- Clinically significant improvement in one or more radicular symptoms or myelopathy at each post-operative time point compared to baseline for the investigational two-level Simplify Disc and the two-level ACDF control group. The data collected will reflect the number of patients who improved (numbers will be stratified to reflect clinical improvement), who remain unchanged, and who deteriorated at each study time point. These endpoints will be graded and defined as follows:
 - Pain questionnaires will be used to evaluate each of the following pain locations:
 - Neck pain
 - Arm pain
 - Left arm pain (investigational group only);
 - Right arm pain (investigational group only);

Success is predicated on maintenance or improvement in neck and arm pain status according to the following equation:

Preoperative Score - Postoperative Score > 0

(Score = pain intensity + pain duration).

- Motor status - A change of one or more grade levels in muscle strength will be regarded as clinically significant.
- Sensory status - Sensation will be graded as normal or abnormal (diminished or absent). Any changes from abnormal to normal or absent to diminished will be regarded as clinically significant improvement.³⁵
- Time to recovery (time to first 15-point NDI improvement).
- Disc height (FSU Height) at each post-operative time point compared to baseline (6 weeks). Both levels have to be a disc height success to claim success for overall disc height. Disc height success for each level is based on either the anterior or posterior measurements meet the following criterions:

Postoperative Height – 6 Week Postoperative Height $\geq -2\text{mm}$

- Adjacent level deterioration at 24 months compared to baseline for the Investigational group.
- Displacement or migration of the device for the Investigational group; only changes of $> 3\text{ mm}$ will be considered significant due to the margin of error in radiographic determination of displacement distances.
- Return to work status postoperative.
- Subject satisfaction and perceived effect at each applicable postoperative timepoint. Success for each satisfaction question (three) will be defined as either a “Definitely True” or “Mostly True” response. Success for the perceived effect will be defined as either a “Completely Recovered,” “Much Improved,” or “Slightly Improved” response.

³⁵ Hacker *et al.*, *supra* note 7.

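### Follow-up after a Simplify Disc is removed is set apart, so later secondary rates in the device arm would rest on subjects who kept the device, and no matching ACDF rule is stated

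*Combined protocol and SAP*

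**What the plan says.** The rule is in section 3.2.5.4.5. Subjects who have one or both Simplify Discs removed stay in the study, but "follow-up subsequent to these events will be summarized separately", provided consent has not been withdrawn. It names the Simplify Disc only. Section 3.2.6.1 defines a removal as "a procedure that removes one or more components of the original implant configuration without replacement with the same type of trial implant", and lists revision, reoperation and supplemental fixation as separate categories.

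For the primary endpoint, section 3.2.6.1 is clear: "All secondary index surgeries will be classified as failures". Section 3.2.6.3 adds parity between the groups, but only for the composite: "The components of the CCS will be evaluated in the same fashion for the ACDF control as they are to be evaluated for Simplify Disc".

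Section 3.2.6.13 opens with improvement in radicular symptoms or myelopathy, assessed "at each post-operative time point compared to baseline for the investigational two-level Simplify Disc and the two-level ACDF control group". It then defines success for pain, SF-36, satisfaction and gait, among others. It does not say how a subject with a secondary index surgery is counted. On the analysis set, section 3.2.6.5 says "Secondary efficacy analyses will be performed using the PP analysis set". That set is defined by the absence of major protocol deviations, and device removal is not named among them. The missing-data rules in section 3.2.6.8 are for the primary composite only.

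**The concern.** Removal of the device is an outcome of treatment. If a subject's later data leave the main tables because the device came out, the remaining device-arm rate is conditional on the device having been kept. It then answers a different question from the rate in all treated subjects, and it sits awkwardly beside a primary endpoint that counts the same subjects as failures.

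The comparison is already non-randomized against a historical control. A selection rule written for one group, with nothing stated for the other, adds a possible asymmetry that propensity score subclassification on baseline variables cannot remove. At stake is how secondary rates at later visits are read. If nothing is changed, the choice of denominator may also be settled only once outcomes are known.

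**Working it through.** The plan gives no figure on this point to reproduce. The check is first a comparison of the text, then an illustration of size.

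**What separate summary means in this plan**

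- Training cases, section 3.2.4.1: "Data from the training set will be summarized separately and not used in the primary comparison to control". Section 3.2.3 likewise sets them apart from the analysis set compared with ACDF.
- Device subjects not selected into a propensity score subclass, section 3.2.6.3: summarized separately, compared with those selected, and taken up in sensitivity analyses. They are outside the primary effectiveness set.
- Training cases and subjects enrolled under the original protocol, section 3.2.6.5: each summarized separately, the latter then compared with the ITT set.

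Each time, the expression describes data held apart from the main comparison set. Section 3.2.5.4.5 uses it for post-removal follow-up, after saying that these subjects will be followed. Exclusion from the main secondary summaries is therefore the natural reading. No readable section returns these subjects to the secondary denominators.

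**Size**

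The documents give neither a removal rate nor a success rate after removal, so all three inputs are assumptions:

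- s = success rate among subjects who keep the device = 80%
- r = share with a removal = 2% or 5% (of 182 enrolled: 0.02 × 182 = 3.6, or 0.05 × 182 = 9.1 subjects)
- q = success rate that removed subjects would show = 0% to 50%

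With removals set aside, the reported rate is s. With everyone counted, it is s(1 − r) + qr. The difference is s − [s(1 − r) + qr] = r(s − q).

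| r | q = 50% | q = 0% |
|---|---|---|
| 2% | 0.02 × 0.30 = 0.6 points | 0.02 × 0.80 = 1.6 points |
| 5% | 0.05 × 0.30 = 1.5 points | 0.05 × 0.80 = 4.0 points |

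The q = 0% column is also the difference from a rule that counts every removal as a non-success. The difference is zero when q = s and changes sign if removed subjects do better than the rest.

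**Cross-check from the other direction**

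Fix the rate with everyone counted at p = 70%. This is the plan's assumed control rate for the composite in section 3.2.6.4, borrowed here only as a base. Setting removals aside gives (p − rq)/(1 − r).

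- r = 1%: 0.70/0.99 = 70.7% with q = 0%, and (0.70 − 0.005)/0.99 = 70.2% with q = 50%. The rise is 0.7 and 0.2 points.
- r = 5%: 0.70/0.95 = 73.7% with q = 0%, and (0.70 − 0.025)/0.95 = 71.1% with q = 50%. The rise is 3.7 and 1.1 points.

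Direction and scale agree.

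**The case against.** The strongest reply is that exclusion is inferred. For training cases the plan adds an explicit statement that the data are not used in the primary comparison. Section 3.2.5.4.5 contains no such statement, and neither the primary effectiveness set nor the per-protocol set lists removal as a reason to leave. This stands as a limit on certainty: exclusion is the natural reading but is not stated. It does not remove the need for a rule, because on any reading the plan leaves open how these subjects count.

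A second reply concerns the control group. A reader might infer that device removals are dropped while comparable ACDF failures stay in. The documents do not support that. Section 3.2.5.4.5 governs prospective follow-up, and only Simplify subjects are followed prospectively, so naming only that device is expected. The controls come from a completed trial whose handling of post-removal data is not given. Sections 3.2.6.11 and 3.2.6.12 are redacted and could bear on the point.

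Third, the scope is narrow. It would be wrong to say that all device failures leave the tables. The rule concerns removals, reoperation and supplemental fixation are not mentioned, and removal with same-type replacement, which section 3.2.6.1 calls a revision, is unclear. Nor is every secondary endpoint exposed to a difference between the groups. Dysphagia, facet deterioration, adjacent-level deterioration and migration are for the investigational group only. For migration and disc height, values after removal no longer describe the implant, and a separate summary is reasonable.

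Finally, secondary endpoints need not follow the composite, and using observed scores after removal is a legitimate alternative to counting failure. That is fair, and it is why a sensitivity analysis on observed scores belongs in the fix. Neither approach sets the subjects aside. Section 3.3.1 repeats that secondary index surgeries are failures and are to be reported accordingly, but it sits in the risk analysis and gives no rule for secondary endpoints.

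**Conclusion.** The concern holds for secondary clinical endpoints. Applied as the plan uses the expression elsewhere, the rule makes later device-arm rates for pain, SF-36, satisfaction and gait conditional on keeping the device. No matching ACDF rule is stated, and control handling is unknown.

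The effect is modest. Under the assumptions shown it is 0.6 to 1.6 points at 2% removals and 1.5 to 4.0 points at 5%. The upper figures are ceilings that require every removed subject to be a non-success. It favors the device only if removed subjects do worse than average. These figures describe the device-arm rate. The effect on the difference between groups also depends on how ACDF removals are treated.

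A reader might take this as a threat to the study's main conclusion. It is not: secondary index surgeries are failures in the composite, its components are evaluated alike in both groups, and sections 3.2.6.3 and 3.2.6.15 keep all investigational subjects in the safety analyses. The readable text attaches no error rate or success criterion to the secondary endpoints.

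**What to change.** Add one rule to section 3.2.6.13 and refer to it from section 3.2.5.4.5:

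> For secondary clinical responder endpoints reported in both groups, a subject in either group whose implant is removed stays in the denominator and counts as a non-success at all visits after the removal. A sensitivity analysis uses the observed scores of these subjects. Their results after removal are also tabulated separately, as a supplement. Device-specific radiographic endpoints, such as migration and disc height, may be summarized separately after removal.

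The text should also say whether a removal with same-type replacement falls under the rule.

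The main analysis should need little new data, because secondary-surgery status is already required for the composite in both groups. The sensitivity analysis for controls depends on the historical trial having collected scores after removal, which the documents do not say. If it did not, the report should state this. The cost is plan wording and slightly less favorable secondary rates.
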